### **7.2.5 Sponsor Responsibility for Reporting Adverse Events**

All Adverse Events will be reported to regulatory authorities, IRB/IECs and investigators in accordance with all applicable global laws and regulations, i.e., per ICH Topic E6 (R1) Guidelines for Good Clinical Practice.

## **7.3 TRIAL GOVERNANCE AND OVERSIGHT**

### **7.3.1 Scientific Advisory Committee**

This trial was developed in collaboration with a Scientific Advisory Committee (SAC). The SAC comprises both Sponsor and non-Sponsor scientific experts who provide input with respect to trial design, interpretation of trial results and subsequent peer-reviewed scientific publications.

### **7.3.2 Executive Oversight Committee**

The Executive Oversight Committee (EOC) comprises members of Sponsor Senior Management. The EOC will receive and decide upon any recommendations made by the external Data Monitoring Committee (eDMC) regarding the trial.

### **7.3.3 Data Monitoring Committee**

To supplement the routine trial monitoring outlined in this protocol, an external Data Monitoring Committee (DMC) will monitor the interim data from this trial. The voting members of the committee are external to the Sponsor. The members of the DMC must not be involved with the trial in any other way (e.g., they cannot be trial investigators) and must have no competing interests that could affect their roles with respect to the trial.

The DMC will make recommendations to the EOC regarding steps to ensure both subject safety and the continued ethical integrity of the trial. Also, the DMC will review interim trial results, consider the overall risk and benefit to trial participants (see Section 8.7 - Interim Analyses) and recommend to the EOC if the trial should continue in accordance with the protocol.

Specific details regarding composition, responsibilities, and governance, including the roles and responsibilities of the various members and the Sponsor protocol team; meeting facilitation; the trial governance structure; and requirements for and proper documentation of DMC reports, minutes, and recommendations will be described in a separate charter that is reviewed and approved by the DMC. The DMC will monitor the trial at an appropriate frequency, as described in the detailed DMC charter. The DMC will also make recommendations to the EOC regarding steps to ensure both subject safety and the continued ethical integrity of the trial.

## 8.0 STATISTICAL ANALYSIS PLAN

This section outlines the statistical analysis strategy and procedures for the trial. If, after the trial has begun, but prior to any unblinding, changes made to primary and/or key secondary hypotheses, or the statistical methods related to those hypotheses, then the protocol will be amended (consistent with ICH Guideline E-9). Changes to exploratory or other non-confirmatory analyses made after the protocol has been finalized, but prior to unblinding, will be documented in a supplemental SAP (sSAP) and referenced in the Clinical Study Report (CSR) for the trial. Post hoc exploratory analyses will be clearly identified in the CSR.

### 8.1 Statistical Analysis Plan Summary

**Key elements of the statistical analysis plan are summarized below; the comprehensive plan is provided in Sections 8.2-8.12.**

Study Design Overview	A Randomized, Active-Controlled, Partially Blinded, Biomarker Select, Phase III Clinical Trial of Pembrolizumab as Monotherapy and in Combination with Cisplatin+5-Flourouracil (5-FU) versus Placebo+Cisplatin+5-FU, as first-line treatment in Subjects with Advanced Gastric or Gastroesophageal Junction (GEJ) Adenocarcinoma	
Treatment Assignment	Approximately 750 subjects with advanced gastric or GEJ adenocarcinoma will be randomized in a 1:1:1 ratio among three treatment arms in this trial, stratified by geographic region, backbone therapy (5-FU vs capecitabine) and disease status (See Section 5.4 Stratification for details). The three treatment arms are as follows:	
	Treatment Arm	Treatment Dose and Schedule
	Treatment Arm 1	Pembrolizumab 200 mg every 3 weeks (Q3W)
	Treatment Arm 2*	Pembrolizumab 200 mg + 5-FU 800 mg/m  /day continuous IV infusion Days 1-5 + Cisplatin 80 mg/m  administrated Q3W
	Treatment Arm 3*	Placebo+5-FU 800 mg/m  /day continuous IV infusion Days 1-5 + Cisplatin 80 mg/m  administrated Q3W
	Although use of 5-FU infusion is preferred, Capecitabine 1000 mg/m  bid Day 1 to Day 14 Q3W may be permitted according to local guideline at Investigator's discretion. Investigator decision regarding the type of comparator used should be determined prior to randomization in the trial. *This is a partially blinded trial. Treatment Arm 1 is open label and Treatment Arm 2 and 3 are blinded.	
Analysis Populations	Efficacy: Intention-to-treat (ITT) population. Safety: All Subjects as Treated (ASaT)	

Primary Endpoint	
1. Progression-free survival (PFS) – per RECIST 1.1 by blinded central radiologists’ review
 
2. Overall Survival (OS)

Statistical Methods for Key Efficacy Analyses	
The primary hypothesis for OS (H2 and H3) and PFS (H1) will be evaluated by comparing pembrolizumab in combination with SOC (cisplatin+5-FU or Capecitabine) versus SOC (cisplatin+5-FU or Capecitabine) using a stratified log-rank test. Estimation of the hazard ratio will be done using a stratified Cox regression model. Event rates over time will be estimated within each treatment group using the Kaplan-Meier method. The primary hypothesis for non-inferiority (H4) of pembrolizumab monotherapy vs. SOC for OS will be evaluated using a stratified Cox regression model. The OS primary hypothesis for superiority (H5 and H6) of pembrolizumab monotherapy vs. SOC will be evaluated using stratified log-rank test.

Statistical Methods for Key Safety Analyses	
The analysis of safety results will follow a tiered approach. The tiers differ with respect to the analyses that will be performed. Safety parameters or adverse experiences of special interest that are identified a priori constitute “Tier 1” safety endpoints that will be subject to inferential testing for statistical significance with p-values and 95% confidence intervals provided for between-group comparisons. Other safety parameters will be considered Tier 2 or Tier 3. Tier 2 parameters will be assessed via point estimates with 95% confidence intervals provided for between-group comparisons; only point estimates by treatment group are provided for Tier 3 safety parameters. The between-treatment difference will be analysed using the Miettinen and Nurminen method.

Interim Analyses	
Two efficacy and one safety interim analyses will be performed in this trial. Results will be reviewed by a DMC. These interim analyses and the final analysis are summarized below. Details are provided in Section 8.7.
 
Safety Interim Analysis
 
 
• Timing: After 10 subjects in each treatment arm have completed one cycle of follow-up. Interim safety monitoring will include review of AE data by the DMC (see Section 8.6.2 for more details on the analyses methods).
 
 
Efficacy Interim Analysis
 
 
▪ Timing: 
 
▪ Interim analysis 1 (IA1) After: 1) all subjects have been enrolled, 2) minimum of 10 months of follow-up and 3) at least 317 OS events are observed among subjects randomized to the SOC and combination arm with PD-L1 CPS1.
 
▪ Interim analysis 2 (IA2): 16 months after the last subject is randomized to the trial and after at least 369 OS events are observed among subjects randomized to the SOC and combination arm with PD-L1 CPS1.
 
 
 
▪ Purpose: 
 
▪ IA1: Interim analysis for PFS (PD-L1 CPS1) (H1) and OS (PD-L1 CPS1 and PD-L1 CPS10) (H2-H6).
 
▪ IA2: Final efficacy analysis for PFS (PD-L1 CPS1) (H1) and interim analysis for OS (PD-L1 CPS1 and PD-L1 CPS10) (H2-H6).
 
 
 
 
Final analysis
 
Timing: at least 22 months after the last subject is randomized to the trial and approximately 415 OS events are observed among subjects randomized to the SOC and combination arm with PD-L1 CPS1.


Multiplicity
	
The multiplicity strategy specified in Section 8.8 will be applied to the primary hypotheses (PFS [PD-L1 CPS1] [H1] and OS [PD-L1 CPS1 and PD-L1 CPS10]) (H2-H6) and the secondary hypothesis (ORR PD-L1 CPS1) (H7) to control the overall Type-I error at 2.5% (one-sided). The graphical approach of Mauer and Bretz [44] will be used. In this approach, when a particular null hypothesis is rejected, the arrow(s) leading to it are removed, and the Type I error allocated to the null hypothesis that was rejected is re-distributed to the other hypotheses.
 
There are three treatment arms in the study. Initially <math>\alpha=0.10\%</math>, <math>1.25\%</math> <math>0.75\%</math> and <math>0\%</math> is allocated to the PFS (PD-L1 CPS1) (H1) , OS(PD-L1 CPS1) (H2), OS (PD-L1 CPS10) (H3) and ORR (PD-L1 CPS1) (H7) hypotheses, respectively, for the Pembrolizumab in combination with SOC versus SOC comparisons and <math>\alpha=0.40\%</math>, <math>0\%</math> and <math>0\%</math> is allocate to OS (non-inf PD-L1 CPS1) (H4), OS (PD-L1 CPS1) (H5) and OS (PD-L1 CPS10) (H6) hypotheses, respectively, for the monotherapy vs. SOC (control) comparisons.

Sample Size and Power
	
The planned sample size is approximately 750 subjects. For PFS (PD-L1 CPS1) (H1), the study has ~91% power to detect a hazard ratio of 0.65 (pembrolizumab in combination with SOC vs. SOC) at <math>\alpha = 0.10\%</math> (one-sided). For OS (PD-L1 CPS1) (H2), the study has ~91% power to detect a hazard ratio of 0.70 (pembrolizumab in combination with SOC vs. SOC) at <math>\alpha = 1.25\%</math> (one-sided). For OS (PD-L1 CPS10) (H3), the study has ~80% (73%) power to detect a hazard ratio of 0.58(0.60) (pembrolizumab in combination with SOC vs. SOC) at <math>\alpha = 0.75\%</math> (one-sided). For the monotherapy vs. SOC comparison of OS (PD-L1 CPS1), the study has ~89% power to establish non-inferiority (H4) (NI margin = 1.2) of pembrolizumab vs SOC at <math>\alpha = 0.40\%</math> (one-sided) if HR = 0.8 and ~82% power (superiority, H5) to detect a hazard ratio of 0.70 at <math>\alpha = 0.40\%</math> (one-sided). For OS (PD-L1 CPS10) (H6), the study has ~80%(63%) power to detect a hazard ratio of 0.58(0.63) (pembrolizumab monotherapy vs. SOC) at <math>\alpha = 0.75\%</math> (one-sided)

**8.2 Responsibility for Analyses/In-House Blinding**

The statistical analysis of the data obtained from this study will be the responsibility of the Clinical Biostatistics department of the SPONSOR.

Although the trial is partially blinded (pembrolizumab mono therapy arm open label and pembrolizumab in combination with standard of care and standard of care arms are blinded) analyses or summaries generated by randomized treatment assignment and actual treatment received will be limited and documented. In addition, the independent radiologist(s) will perform the central imaging review without knowledge of treatment group assignment.

The SPONSOR will generate the randomized allocation schedule(s) for study treatment assignment for this protocol, and the randomization will be implemented in IVRS.

The DMC will serve as the primary reviewer of the unblinded results of the interim analysis and will make recommendations for discontinuation of the study or modification to an

executive oversight committee of the SPONSOR. Depending on the recommendation of the DMC, the Sponsor may prepare a regulatory submission. If the DMC recommends modifications to the design of the protocol or discontinuation of the study, this executive oversight committee and limited additional sponsor personnel may be unblinded to results at the treatment level in order to act on these recommendations. Additional logistical details, revisions to the above plan and data monitoring guidance will be provided in the DMC Charter.

### **8.3 Hypotheses/Estimation**

Objectives and hypotheses of the study are stated in Section 3.0.

### **8.4 Analysis Endpoints**

#### **Primary Efficacy Endpoints**

##### **Progression-free survival (PFS) – RECIST 1.1 by blinded central radiologists’ review**

PFS is defined as the time from randomization to the first documented disease progression per RECIST 1.1 based on blinded central radiologists’ review or death due to any cause, whichever occurs first. See Section 8.6.1 for definition of censoring.

##### **Overall Survival (OS)**

OS is defined as the time from randomization to death due to any cause. Subjects without documented death at the time of the final analysis will be censored at the date of the last follow-up.

#### **Secondary Efficacy Endpoint**

##### **Overall Response Rate (ORR) – RECIST 1.1 by blinded central radiologists’ review**

ORR is defined as the proportion of the subjects in the analysis population who have a CR or partial response (PR).

### **8.5 ANALYSIS POPULATIONS**

#### **8.5.1 Efficacy Analysis Populations**

The Intention-to-Treat (ITT) population will serve as the population for primary efficacy analysis. All randomized subjects will be included in this population. Subjects will be included in the treatment group to which they are randomized. Details on the approach to handling missing data are provided in Section 8.6 Statistical Methods.

## **8.5.2 Safety Analysis Populations**

The All Subjects as Treated (ASaT) population will be used for the analysis of safety data in this study. The ASaT population consists of all randomized subjects who received at least one dose of study treatment. Subjects will be included in the treatment group corresponding to the study treatment they actually received for the analysis of safety data using the ASaT population. For most subjects this will be the treatment group to which they are randomized. Subjects who take incorrect study treatment for the entire treatment period will be included in the treatment group corresponding to the study treatment actually received. Any subject who receives the incorrect study medication for one cycle but receives the correct treatment for all other cycles will be analysed according to the correct treatment group and a narrative will be provided for any events that occur during the cycle for which the subject is incorrectly dosed.

At least one laboratory or vital sign measurement obtained subsequent to at least one dose of study treatment is required for inclusion in the analysis of each specific parameter. To assess change from baseline, a baseline measurement is also required.

## **8.6 STATISTICAL METHODS**

### **8.6.1 Statistical Methods for Efficacy Analyses**

This section describes the statistical methods that address the primary and secondary objectives. Methods related to exploratory objectives and exploratory endpoints will be described in the supplemental statistical analysis plan (sSAP), this includes the ePRO data described in Section 7.1.2.9.

Efficacy results that will be deemed to be statistically significant after consideration of the Type I error control strategy are described in Section 8.8, Multiplicity and Section 8.7 Interim Analysis. Nominal p-values will be provided for other efficacy analyses, but should be interpreted with caution due to potential issues of multiplicity.

### **Progression-free Survival (PFS)**

The non-parametric Kaplan-Meier method will be used to estimate the PFS curve in each treatment group. The treatment difference in PFS will be assessed by the stratified log-rank test. A stratified Cox proportional hazards model with Efron's method of tie handling will be used to assess the magnitude of the treatment difference (ie, hazard ratio) between the treatment arms. The hazard ratio and its 95% confidence interval from the stratified Cox model with Efron's method of tie handling and with a single treatment covariate will be reported. Geographic region, backbone therapy (5-FU or Capecitabine) and disease status will be used as the stratification factors in both the stratified log-rank test and the stratified Cox model.

Since disease progression is assessed periodically, PD can occur any time in the time interval between the last assessment where PD was not documented and the assessment when PD is documented. For the primary analysis, for the subjects who have PD, the true date of disease progression will be approximated by the date of the first assessment at which PD is

objectively documented per RECIST 1.1, regardless of discontinuation of study drug. Death is always considered as a confirmed PD event. Subjects without documented PD/death will be censored at the last disease assessment date.

In order to evaluate the robustness of the primary endpoint PFS per RECIST 1.1 by blinded central radiologists' review, we will perform two sensitivity analyses with a different set of censoring rules. The first sensitivity analysis is the same as the primary analysis except that it censors at the last disease assessment without PD when PD or death is documented after more than one missed disease assessment. The second sensitivity analysis is the same as the primary analysis except that it considers discontinuation of treatment or initiation of an anticancer treatment subsequent to discontinuation of study-specified treatments, whichever occurs later, to be a PD event for subjects without documented PD or death. The censoring rules for primary and sensitivity analyses are summarized in [Table 12](#) below.

**Table 12** Censoring Rules for Primary and Sensitivity Analyses of PFS

Situation	Primary Analysis	Sensitivity Analysis 1	Sensitivity Analysis 2
No PD and no death; new anticancer treatment is not initiated	Censored at last disease assessment	Censored at last disease assessment	Censored at last disease assessment if still on study therapy; progressed at treatment discontinuation otherwise
No PD and no death; new anticancer treatment is initiated	Censored at last disease assessment before new anticancer treatment	Censored at last disease assessment before new anticancer treatment	Progressed at date of new anticancer treatment
PD or death documented after $\leq 1$ missed disease assessment	Progressed at date of documented PD or death	Progressed at date of documented PD or death	Progressed at date of documented PD or death
PD or death documented after $\geq 2$ missed disease assessments	Progressed at date of documented PD or death	Censored at last disease assessment prior to the $\geq 2$ missed disease assessment	Progressed at date of documented PD or death

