### **4.2.3 Rationale for Endpoints**

#### **4.2.3.1 Rationale for Efficacy Endpoints**

##### **4.2.3.1.1 Primary Efficacy Endpoints**

Although OS is the gold standard for a “hard endpoint” in clinical studies in the area of oncology, OS as a primary endpoint for a 1st line gastric trial with PD-1/ PD-L1 pathway inhibitors may be extremely difficult to achieve. In US/ EU, gastric cancer is a rare tumour type and most subjects have advanced or metastatic disease at the time of diagnosis. Because of the limited number of subjects in western countries and the multiple companies developing this class of drugs for gastric cancer, it is expected that there will be a high cross over rate for the chemotherapy arm subjects. Therefore, this trial will use a dual endpoint of OS and PFS. PFS is an acceptable scientific endpoint for a randomized Phase III trial to demonstrate superiority of a new antineoplastic therapy. RECIST 1.1 will be used to determine the dates of progression as this methodology is accepted by regulatory authorities. Because the treatment assignment is unblinded for pembrolizumab monotherapy, images will be read by central radiologists blinded to treatment assignment to minimize bias in the response.

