Serum carcinoembryonic antigen (CEA) o		X			X		X	X o				
Serum CA19-9 o		X			X		X	X o				
Laboratory Procedures/Assessments: Analysis performed by CENTRAL laboratory												
Blood for Genetics p			X									
Correlative Blood Samples (DNA) q			X	X	X				X			
Correlative Blood Samples (RNA) q			X	X	X				X			
Correlative Blood Samples (plasma) q			X									
Correlative Blood Samples (serum) q			X									
Efficacy Measurements												
Tumour Imaging r		X			X		X	X	X s		X s	
Tumour Tissue Collection												
Archival and/or Newly Obtained Tissue Collection t	X								X			

- a. Unless otherwise specified, assessments/procedures are to be performed on Day 1 and prior to the first dose of treatment for each cycle unless otherwise specified.
- b. In subjects who discontinue study therapy without documented disease progression, every effort should be made to continue monitoring their disease status by radiologic imaging every 6 weeks ( $\pm$  7 days) until (1) the start of new anti-cancer treatment, (2) disease progression as assessed by the central imaging vendor, (3) death, or (4) the end of the study, whichever occurs first.
- c. After documented local site assessed disease progression or the start of new anticancer treatment; contacts are approximately every 12 weeks by telephone. Updated survival status may be requested by the Sponsor at any time during the course of the study. Upon Sponsor notification all subjects who do not /will not have a scheduled study visit or study contact during the Sponsor defined time period will be contacted for their survival status (excluding subjects that have a death event previously recorded).
- d. Unless otherwise specified, the window for each visit is  $\pm$  3 days. Cycle 1 treatment should be given within 3 days of randomization.
- e. Written consent must be obtained prior to performing any protocol specified procedure. Results of a test performed prior to the subject signing consent as part of routine clinical management are acceptable in lieu of a screening test if performed within the specified time frame (eg, within 21 days prior to the first dose of trial treatment). Screening number will be assigned when the study informed consent is signed.

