#### PFS:

At the final PFS-PD-L1 CPS1 (H1) analysis (IA2), approximately 16 months after the last subject is randomized approximately 430 PFS events will be accumulated in the combination therapy arm and control arm. With 430 events, the study has ~91% power to detect a hazard ratio of 0.65 (pembrolizumab in combination with SOC vs. SOC) at alpha = 0.10% (one-sided). The sample size calculation is based on the following assumptions: 1) progression-free survival follows an exponential distribution with a median of 6 months in the control arm, 2) an enrollment period of 19 months, and 3) a yearly dropout rate of 5%.

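### PFS Sensitivity Analysis 2 dates a switch to new anticancer treatment by later vital status: without documented PD, a switcher who later dies is scored at death, one still alive at the switch

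*Combined protocol and SAP*

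**What the plan says.** Section 8.6.1 offers two checks on the robustness of centrally reviewed PFS: "we will perform two sensitivity analyses with a different set of censoring rules". SA2 is the primary analysis with one change. Stopping study treatment, or starting another anticancer therapy afterwards, is taken, "whichever occurs later, to be a PD event for subjects without documented PD or death".

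Table 12 says the same. In the row "No PD and no death; new anticancer treatment is initiated", SA2 gives "Progressed at date of new anticancer treatment". In the row without new treatment, SA2 scores an event at treatment discontinuation unless the subject is still on study therapy. In the two rows where PD or death is documented, SA2 uses the PD or death date, exactly as the primary analysis does. Neither row asks whether new treatment had begun earlier.

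Footnote b to the flow charts (6.1.1 and 6.1.2) keeps imaging going in subjects who stop without progression "until (1) the start of new anti-cancer treatment, (2) disease progression as assessed by the central imaging vendor", or until death or the end of the study. Section 7.1.2.6.2 also stops imaging at new treatment. Section 7.1.5.3.3 continues survival contacts about every 12 weeks after a switch. Deaths after a switch are therefore collected, while PD after a switch mostly is not.

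**The concern.** For a subject who switches without documented PD, the next documented event will usually be death. SA2 then does nothing: the subject keeps the death date, as in the primary analysis. Only a switcher who is still alive at the cut-off is scored at the switch. The rule looks ahead to a later outcome in order to date an earlier event, and it ranks the subjects the wrong way round.

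SA2 is useful to the extent that it departs from the primary analysis where subjects switch. If most switchers have died by the final PFS analysis (the second interim analysis, IA2), the two analyses coincide for most of them. Agreement could then be reported as robustness of H1 to switching when it comes largely from the scoring rule.

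**Working it through.** **1. The plan's own figures.** Inputs from section 8.9: "approximately 430 PFS events will be accumulated in the combination therapy arm and control arm", HR 0.65, one-sided alpha 0.10%, control median 6 months (exponential), 19 months' enrolment, 16 months' follow-up after the last randomisation, 5% yearly dropout, about 250 subjects per arm.

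- Power (Schoenfeld) = Φ(|ln 0.65| × √430 / 2 − 3.090) = Φ(0.4308 × 10.368 − 3.090) = Φ(1.376) = 0.916. The plan states about 91%.
- Expected events at IA2, with follow-up uniform from 16 to 35 months, event hazards ln 2/6 and 0.65 × ln 2/6, and dropout hazard −ln(0.95)/12: 250 × 0.908 + 250 × 0.809 ≈ 429. The plan states about 430.

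Both reproduce.

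**2. The rule applied to two subjects.** Both switch at month 4 without documented PD. A is alive at the cut-off; B dies at month 12.

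| Rule | A | B |
|---|---|---|
| Primary | censored at last scan before month 4 | event at 12 |
| SA2 as written | event at 4 | event at 12 |
| Every switch dated at the switch | event at 4 | event at 4 |

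**3. Ceiling on what SA2 can rescore.** SA2 departs from the primary analysis only where neither PD nor death is documented. At IA2 that is about 500 − 430 = 70 subjects. This is an upper limit on rescoring, not a count of the subjects affected by the fault.

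**4. Share of switchers already dead at IA2.** The documents give no switch time or post-switch survival, so these are assumptions. With a switch at month t and post-switch median m, the share is the average of 1 − exp(−(ln 2/m)(F − t)) over F from 16 to 35 months.

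- t = 4.5, m = 10: 1 − (e^−0.797 − e^−2.114)/(0.0693 × 19) = 1 − 0.250 = 75%.
- t = 9, m = 14.3: 54%.
- t = 3, m = 5: 94%.

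Over this range, 54% to 94% of switchers without PD keep the death date under SA2.

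**5. Effect on the hazard ratio.** Simulation of 200,000 per arm with planning medians 6 and 6/0.65 months. The switch is uniform between randomisation and the would-be PD date, imaging ends at the switch, post-switch median survival is 7 months, and follow-up is 16 to 35 months. Dropout, and stopping treatment without new therapy, are not modelled.

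| Switching, control / combination | Primary | SA2 as written | Every switch at its date |
|---|---|---|---|
| 10% / 10% | 0.660 | 0.664 | 0.662 |
| 20% / 20% | 0.672 | 0.678 | 0.672 |
| 20% / 10% | 0.681 | 0.674 | 0.629 |
| 10% / 20% | 0.651 | 0.668 | 0.707 |
| 30% / 10% | 0.703 | 0.684 | 0.597 |

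For a 10-point imbalance, the gap between the last two columns is 0.674 − 0.629 = 0.045 one way and 0.707 − 0.668 = 0.039 the other. SA2 as written covers 0.007/0.052 = 13% and 0.017/0.056 = 30% of the distance from the primary analysis. With 20% switching in control, the control median is about 6.6 months as written and 5.1 months with every switch dated at the switch.

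**The case against.** **SA1 also bears on these subjects.** A reader might infer that SA2 is the only planned check and that switching goes wholly untested. The documents do not support that. SA1 censors PD or death that follows two or more missed assessments. If scans not done after the switch count as missed, B falls there: eight months is about 35 weeks, or five six-weekly time points. In the simulation the median gap from switch to death was about 5.5 months (some 24 weeks), so most such deaths would be censored. The plan does not say whether those scans count as missed, and SA1 never scores a switch as an event. SA1 is therefore a different check, but a real one.

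**Switching before central PD is not documented as heavy.** Section 4.2.3.1.1 says "it is expected that there will be a high cross over rate for the chemotherapy arm subjects", and a reader might take this as a forecast of the switching at issue. It explains why OS is difficult as an endpoint and gives no rate. A switch after central PD cannot change PFS under any of these rules. Immediate central verification of site-assessed PD (7.1.2.6.5) should also limit early switching. Routes remain, since section 2.1 lets treatment end for clinical progression, adverse events or investigator decision. Section 5.2.1.2 treats the two blinded arms differently once chemotherapy is stopped for toxicity. An imbalance is possible, but its size is unknown.

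**SA2 may be meant only to stress the censoring.** Scoring events only for otherwise censored subjects is a recognised device, and counting every switch gives a different, composite endpoint. The stated purpose is general robustness, so testing switching is an inference from SA2's content. This limits what SA2 can be said to have failed at. It does not remove the dependence on later vital status.

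**Status at the switch.** One could read the no-PD, no-death condition as status when the switch occurs. A switcher who later dies would then fit two rows of Table 12 with conflicting scores. The primary column would also censor deaths that section 8.6.1 says always count. The text does not bear that reading.

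**Conclusion.** The point holds as a fault in the written rule. Among switchers without documented PD, SA2 repeats the primary result for those who die and rescores only those alive at the cut-off. Agreement between the two analyses is therefore weak evidence about switchers who die.

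The size rests on assumed switching rates, switch times and post-switch survival. Balanced switching barely moves the hazard ratio (0.678 against 0.672). A 10-point imbalance moves it by about 0.04 to 0.05. The direction depends on which arm switches more: as written, SA2 is conservative when control switches more and flattering when the combination arm does. No illustrated value crosses 0.735, the approximate hazard ratio at the H1 bound at IA2 (Table 15), and SA2 has no alpha or decision role.

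A reader might take 70 of 500 (14%) as the measure of the fault. It is not, because many of the 430 events will be central PD before any switch, and the number of switchers without PD who die cannot be derived from the documents. Severity is minor to moderate.

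**What to change.** In section 8.6.1 and the SA2 column of Table 12, define the SA2 event as the earliest of documented PD, death and the SA2 rescoring date, whether or not PD or death is documented later. The rescoring date is the start of new anticancer treatment or, where none is started, treatment discontinuation, as the first row of Table 12 already has it. Remove from the text the restriction to subjects without PD or death. In the two rows with documented PD or death, score SA2 at the rescoring date if it comes first, and otherwise at the PD or death date. Naming discontinuation keeps these rows consistent with the first row. Leave the primary analysis and SA1 unchanged.

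The edit is one sentence and two table cells, using dates already collected. If the sponsor regards SA2 as non-confirmatory, section 8.0 allows the change in the supplemental SAP before unblinding. The price is that SA2 medians shorten (6.6 to 5.1 months in control in the 20% example) and the SA2 hazard ratio may be less favourable. The change also brings forward the event for subjects who stop, start nothing new, and later have documented PD or die; the simulation does not cover them.
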